#### Interim analysis

In addition to routine data reviews of safety data an early evaluation of the treatment effect at the interim analysis will be implemented at the time when 50% of the total number of subjects will have 2 or more longitudinal observations per subject. A non-binding recommendation of early stopping for efficacy will be suggested to the DSMB if the estimate of the treatment effect obtained at the interim analysis is positive and the corresponding one-sided p-value is lower than a small reference value (corresponding to the value of the O'Brien-Fleming spending

function at the information fraction of 0.5). A non-binding recommendation of early stopping for futility will be suggested based on the conditional power analysis.

In the absence of the suggestions for early stopping or in the case when the DSMB decides to overrule the suggested stopping, the study is continued and treatment efficacy is evaluated at the second look (after completion of the study). Further details could be found in SAP.

### Safety

It is possible that the DSMB may recommend stopping the trial early due to safety concerns. To monitor safety, adverse event rates will be compared between the two trial arms and reported to the DSMB. Early stopping rules are only guidelines; the DSMB may take a more global view of the trial during data monitoring. Provide this broader perspective, the DSMB reports will include summaries of accrual, patient characteristics, adverse events, compliance rates with therapy, frequency of protocol violations, data quality, primary and secondary endpoints, other information as requested by the DSMB, and any unanticipated special problems that arise during the conduct of the trial.

## 8.5 Queried/Missing Data Procedures

Consistency checks and range checks will be built into the data management system. This will allow many errors to be identified and corrected at the time of data entry. Additional queries regarding any problems with data will be sent to site coordinators regularly throughout the course of the study. Sites will also be monitored during the study, especially for late entry/editing of data, missing data and protocol violations/deviations. Any data which are judged by the medical monitors to be or unattainable or unverifiable, and which cannot be resolved, will be set to missing.

The study report will indicate the number of participants who have missing data on each study endpoint. For covariate-adjusted analyses, the number of participants who have missing data on the covariates will be reported. All analyses will be participanted to sensitivity checks to determine what, if any, consequences arise as a result of missing data in the trial. If the missing data are deemed consequential (i.e. they either result in clinically meaningful changes in estimates of effects or in statistically significant changes in estimates of effects or if they appear to result from informative sources and/or induce bias in the analysis) multiple approaches to addressing the missing data will be applied with further sensitivity analyses and analysis of assumptions to select an appropriate method which may include simple approaches (e.g. imputation of last-observation- or last-rank-carried-forward) to model-based approaches (e.g. pattern-mixture models) to multiple imputation, with compensatory adjustments made to the analytic methods as appropriate.

Throughout the study, the rate, timing, and reasons for participant withdrawal will be monitored by site and treatment arm. Any site with a pattern of differential withdrawal by treatment arm will be queried. If necessary, retraining will take place or the site may be barred from enrolling additional participants to the study.

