## 8.1.1 Analysis of the Primary Outcome

The analytic approach for the Primary Outcome is summarized here. The detailed plan for all planned outcomes is provided in the Statistical Analysis Plan (SAP).

Primary Aim: To compare the effect of pitavastatin versus placebo on vascular measures in at least 354 adolescents with excess adiposity (body mass index [BMI] ≥85th percentile) and CDO (defined as high non-HDL-C + high TG/HDL-C ratio).

**Primary Hypothesis:** Over 2 years of observation, participants in the pitavastatin group will have a significantly different change over time (slope) in pulse wave velocity (PWV) than participants in the placebo group.

**Study Measures:** Pulse wave velocity (PWV); secondary measures include carotid intima media thickness (CIMT) and carotid artery stiffness.

**Primary Analysis:** Change in each of the vascular variables will be compared between groups across all study time points using SAS for Windows® (SAS Institute, Cary, NC).

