### **Assumptions:**

- 1. Baseline pulse wave velocity (PWV) is normally distributed with a mean of 6.3 m/sec and a standard deviation of 1.1 m/sec.
- 2. In addition to the baseline PWV measurement, PWV will be measured at after six months, 12 months, and 24 months.
- 3. Any change in PWV over the two-year duration of the study is conservatively assumed to be linear in time (i.e., 25% of the change will be observed at the six month visit, 50% of the change will be observed at the 12 month visit, and 100% of the change will be observed at the 24 month visit).
- 4. The following 3 hypotheses (scenarios) are considered:
  - a. In Scenario 1, the PWV will remain unchanged in the control group over the twoyear duration of the study and will decrease 8% in the statin group over the same 2-year period.
  - b. In Scenario 2, the PWV will decrease 5% in the control group over the two-year duration of the study and will decrease 11% in the statin group over the same 2-year period.

- c. In Scenario 3, the PWV will remain unchanged in the control group over the twoyear duration of the study and will decrease 5% in the statin group over the same 2-year period.
- 5. The within-participant correlation between any pair of PWV measurements is assumed to be 0.5.
- 6. The sample size is adjusted by 20% to account for participant dropout.
- 7. The effect of crossover has not been incorporated into these sample size calculations.

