## **Sample Size Calculations:**

The mean slope (change) over two years of follow-up can be calculated as:

$$\mu_{s} = \overline{PWV}_{24} - \overline{PWV}_{0}$$

Where  $\overline{PWV_0}$  and  $\overline{PWV_{24}}$  are the mean PWV at baseline and 24 months, respectively.

The variance of the slope over two years of follow-up can be calculated as:

$$\sigma_s^2 = \frac{\sigma^2}{SS_t} (1 - \rho)$$

Where  $\sigma$  is the standard deviation of PWV (assumed to be constant over time for the purposes of these calculations),  $\rho$  is the within-participant correlation between pairs of PWV measurements,  $SS_t = \sum (t_i - \bar{t})^2$ , and  $t = \{0, 0.25, 0.5, 1\}$  (since the assumed changes were given over two years of observation, it is easier to use this formulation for time).

After calculating the mean slopes for both the control and statin groups and the standard deviation of the slope, the Inequalities Tests for Two Means (Two-Sample t-Test) module of PASS was used to calculate the required sample size assuming a two-sided type 1 error rate of 5% and 85% power. The sample sizes required under each of the three scenarios are listed as follows:

Scenario	$\Delta_c$	$\Delta_t$	$Slope_c$	$Slope_t$	$\sigma_s$	N/group
1	0%	8%	0	-0.504	1.052	100
2	5%	11%	-0.315	-0.693	1.052	177
3	0%	5%	0	-0.315	1.052	253

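### Section 8.5 lets the missing-data method behind the reported result be chosen after several have been run, and lists last observation carried forward, which does not suit a slope endpoint

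*Protocol*

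**What the plan says.** Section 8.5 subjects all analyses to checks on the consequences of missing data. The next step opens "If the missing data are deemed consequential (i.e. they either result in clinically meaningful changes in estimates of effects", and two further triggers follow: statistically significant changes in the estimates, and signs that the missingness is informative or induces bias. If any applies, several approaches are tried, with further sensitivity analyses and an examination of assumptions, "to select an appropriate method which may include simple approaches (e.g. imputation of last-observation- or last-rank-carried-forward) to model-based approaches". The list continues with pattern-mixture models and multiple imputation, and allows the analytic methods to be adjusted to compensate.

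The section names no primary missing-data method or assumption, sets no order among the methods, and does not limit any of them to sensitivity use. Unlike 8.1, 8.1.1 and 8.4, it does not refer to the SAP. Section 4.2.4 relies on 8.5 to detect and minimize bias.

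The primary hypothesis (2.1 and 8.1.1) concerns the slope of pulse wave velocity (PWV) over two years, measured at 0, 6, 12 and 24 months (4.3.1). Section 8.2 describes a repeated-measures analysis with participant and site random effects, and its sample size allows for 20% drop-out.

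**The concern.** Two separate matters are at stake.

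The first is the choice of method. A confirmatory test holds its level when the analysis is fixed before the estimates are seen. Here two triggers depend on the treatment estimate itself, and a method is then chosen with several results in view. Nothing stops the chosen method from supplying the headline result.

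The second is the list. LOCF assumes no change after the last visit seen. For an endpoint that is a rate of change, this replaces part of each drop-out's slope with zero. Last rank carried forward turns the comparison into one of ranks, so it does not estimate the slope difference that the hypothesis names. Neither is needed, because the repeated-measures model of 8.2 uses every observed visit without filling in values.

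**Working it through.** **Inputs from section 8.2.** PWV is "normally distributed with a mean of 6.3 m/sec and a standard deviation of 1.1 m/sec". "The within-participant correlation between any pair of PWV measurements is assumed to be 0.5". The second scenario assumes that "the PWV will decrease 5% in the control group over the two-year duration of the study and will decrease 11% in the statin group". On a 6.3 m/sec baseline these changes are -0.315 and -0.693 m/sec, a difference of -0.378. Also, "Any change in PWV over the two-year duration of the study is conservatively assumed to be linear in time", with t = {0, 0.25, 0.5, 1}.

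**The plan's own figure.** The mean of t is 0.4375, so SS_t = 0.1914 + 0.0352 + 0.0039 + 0.3164 = 0.5469. The slope SD is √(1.1² × 0.5 / 0.5469) = 1.052, as stated. "assuming a two-sided type 1 error rate of 5% and 85% power", a two-sample t-test needs 141 completers per group, and 141 / 0.80 = 176.25, rounded up to 177. The stated figure reproduces.

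**Slope kept under LOCF.** The least-squares slope is Σ(tᵢ − 0.4375)yᵢ / 0.5469. For a true slope of 1, with the last value carried forward:

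| Last visit | Carried-forward profile | Slope kept |
|---|---|---|
| Baseline | 0, 0, 0, 0 | 0 |
| Month 6 | 0, 0.25, 0.25, 0.25 | 0.25 × 0.4375 / 0.5469 = 0.200 |
| Month 12 | 0, 0.25, 0.5, 0.5 | (−0.0469 + 0.3125) / 0.5469 = 0.486 |

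**Equal 20% drop-out, true difference 6%.** The protocol does not give the timing, so the range is shown.

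| Timing (assumed) | Share of effect kept | Difference |
|---|---|---|
| All after baseline | 0.80 | 4.8% |
| Evenly spread | 0.80 + 0.20 × 0.229 = 0.846 | 5.1% |
| All after month 12 | 0.80 + 0.20 × 0.486 = 0.897 | 5.4% |

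Here 0.229 is the mean of 0, 0.200 and 0.486. In m/sec, the evenly spread case turns -0.378 into -0.320.

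**Unequal drop-out (assumed rates, evenly spread).** Each arm keeps 1 − d × (1 − 0.2286) of its slope, which is 0.923 at d = 10% and 0.769 at d = 30%.

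- 10% placebo, 30% statin: −0.693 × 0.769 + 0.315 × 0.923 = −0.242, or 0.64 of the true difference.
- 30% placebo, 10% statin: −0.693 × 0.923 + 0.315 × 0.769 = −0.397, or 1.05 of it.
- No drug effect, both arms at −0.315, 10% versus 30%: 0.315 × (0.923 − 0.769) = 0.049 m/sec, or 0.049 / 6.3 = 0.8 percentage points of spurious difference.
- No drug effect, equal drop-out: zero.

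**Simulation.** There were 177 per arm and 4,000 replicates, with constant correlation 0.5 and drop-out at random and evenly spread. Four methods were compared: complete-case slopes, the likelihood repeated-measures slope (covariance taken as known), LOCF slopes, and last rank carried forward.

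| Drop-out, placebo/statin | Quantity | Likelihood | LOCF | Last rank | Smallest of four p-values |
|---|---|---|---|---|---|
| 20/20, true −0.378 | Mean estimate | −0.379 | −0.320 | – | – |
| 20/20, true −0.378 | Power | 0.88 | 0.84 | 0.79 | – |
| 10/30, true −0.378 | Power | 0.87 | 0.60 | 0.78 | – |
| 20/20, no effect | Rejection | 0.047 | 0.050 | 0.048 | 0.079 |
| 10/30, no effect | Rejection | 0.044 | 0.072 | 0.048 | 0.107 |

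The last column counts a two-sided rejection in either direction. Complete-case analysis is not named in 8.5, and the pattern-mixture and multiple-imputation options were not simulated, so this column illustrates scale only.

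**The case against.** The strongest reply is that 8.5 is a contingency. LOCF appears only as an example of what may be used, beside sound alternatives, and only once missingness is judged consequential. One trigger, informative missingness, does not depend on the estimate, and the choice is to be informed by examining assumptions. The default is the repeated-measures model, and the SAP, which is not among the documents at hand, may already fix it. Participants who stop study drug permanently are still measured to 24 months (5.3.1), 5.4 calls 20% drop-out conservative, and 8.5 monitors withdrawal by arm and acts on sites where it differs. At equal 20% drop-out, LOCF attenuates the effect and costs little power.

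Much of this stands, and it rules out three stronger readings that a reader might infer.

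- *That the protocol prescribes choosing by result, and so abandons type I error control.* It does not say that the p-value decides. The 8% to 11% figures come from always choosing the smallest p-value.
- *That both carry-forward methods bias the slope test.* The slope arithmetic applies to LOCF. Last rank changes what is estimated, but held its level in simulation.
- *That LOCF will create a false benefit.* With equal drop-out and no effect it creates none. With unequal drop-out the direction varies, and the protocol gives no reason to expect a 10%/30% split.

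What the reply does not answer is that 8.5 states its own rule without deferring to the SAP, and leaves a carried-forward result eligible to become the primary one.

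**Conclusion.** The point holds as a defect in a stated rule. It is not a complaint about detail left to the SAP. Section 8.5 permits a result-dependent choice of method for the primary comparison, so the nominal 5% is not guaranteed, with about 8% to 11% as an illustrative worst case. It also admits LOCF, which at the planned drop-out would cut a 6% difference to about 5.1% (4.8% to 5.4%) and, under unequal drop-out, could bias it either way.

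These sizes rest on the protocol's linear change and 0.5 correlation, and on assumed drop-out timing and arm-specific rates. The simulations use random drop-out only, so they say nothing about how any method performs when drop-out is informative. The matter should be corrected, but it does not undermine the design.

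**What to change.** In 8.5, state that the primary analysis is the repeated-measures random-effects slope model of 8.2, fitted by likelihood to all observed visits under a missing-at-random assumption, and that it stays primary whatever the sensitivity results show. Remove LOCF and last rank carried forward as candidates for the primary result. Replace the trigger-and-select step with a fixed sensitivity set, for example pattern-mixture models or multiple imputation with delta adjustment, always run and reported beside the primary result and never in place of it. If the SAP already does this, bring 8.5 into line with it.

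The cost is a wording change and a small amount of extra analysis. Sample size, visits and data collection are unaffected.

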## 8.6 Participants to be Included in Analyses

All participants who remain eligible for and enrolled in the trial will be included in the analysis and their data will be analyzed by intention-to-treat in the group to which they were randomized unless otherwise specified.

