#### 4.2.3 Masking

The participant's treatment assignment (pitavastatin versus placebo) will be obtained from the randomization computer at the DCC by the responsible pharmacist. The pitavastatin and placebo pills will be identical in size and shape, ensuring that neither participant nor investigator will be able to determine the treatment assignment. Participants, parents, providers and investigators will be masked to study assignment during the trial. Only designated DCC staff and site research pharmacists will be aware of treatment assignment. Given the relatively low side-effect profile of pitavastatin, it is unlikely, although not impossible, that patients will be able to guess their treatment assignment. All study measures will be obtained without knowledge of the participant's treatment assignment.

Because of the anticipated difference in lipid results between the two groups, knowledge of the full results of fasting lipid profiles would result in unmasking. However, knowledge of TG and HDL-C results are useful in informing lifestyle counseling, and extremely elevated TGs are a safety measure. Knowledge of these results would not be anticipated to result in unmasking, as these values have not been significantly impacted by statins in pediatric trials. For these reasons and for quality control purposes, fasting lipid profiles will be assessed in a centralized core lab, and results of TG and HDL-C only will be shared with the study center team and participants. LDL-C levels will be monitored by the core lab, and if the value is ≥160 mg/dL for more than six months on two successive measures, the DCC and site PI will be informed. This is anticipated to be a rare event, although it may result in a decision to discontinue study drug and start statin therapy based on clinical recommendations (see **Section 6.2.2**). The participant will continue to be enrolled in the trial and have all study measures, as per intention to treat.

Likewise, results from NMR lipoprotein fractions performed in the core lab will not be shared with study sites until all participants at all sites have completed the trial.

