Study drug will be discontinued for each of these issues; however, there will be no unmasking until the end of the study unless requested by the DSMB or emergency situations. Consideration for withdrawal will trigger review by the Medical Monitor. The study drug may be restarted if the reason for cessation is liver or muscle inflammation and improves within 4 weeks; however, if the reason for cessation recurs within 4 weeks of re-initiation, the study drug will be stopped permanently. The reasons for temporary and permanent discontinuations of study drug will be documented. If the study drug is permanently discontinued, the participant will continue to be followed on the diet and lifestyle restrictions and undergo expected tests and measurements through the planned completion date (24 months after randomization), unless indication for withdrawal from trial is also met (see below).

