## 5.3.2 Participant Withdrawal from the Trial

Participants may be withdrawn from the trial for the following reasons:

- Written participant/guardian refusal to continue in the trial, including refusal of the participant to sign the adult informed consent form upon reaching the age of consent.
- Participant non-compliance with study visits, assessments and study drug such that data
  from that participant are absent or of poor validity, despite every effort being made by
  site staff. The decision to withdraw a participant for non-compliance will be made jointly
  with the site investigators, DCC, and the study PI; input from the DSMB may also be
  sought. Reasons for withdrawal will be carefully recorded.
- Participant is diagnosed with an eating disorder.
- Participant develops a medical or psychiatric condition that precludes full participation in study interventions and measures.
- Participant undergoes bariatric surgery.

The reason and the circumstances of withdrawal will be documented for all participants withdrawn from the study.

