### 8. STATISTICS

## 8.1 Statistical Analysis Plan

The primary analytic approach for all trial outcomes will be intention-to-treat (ITT). Several secondary analytic approaches will also be examined as outlined below and discussed in detail in a separate Statistical Analysis Plan (SAP).

- Non-intention-to-treat (NITT): Participants will be classified according to treatment
  actually received. NITT analyses, while potentially more powerful due to less dilution of
  treatment effect compared to an ITT analysis, are subject to bias because the inherent
  balance and lack of bias provided by randomization in measured and unmeasured
  patient characteristics of the two treatment groups is not preserved.
- Non-intention-to-treat by duration of pitavastatin use: If a substantial fraction of
  participants either cross-over from placebo to pitavastatin or are prescribed open-label
  pitavastatin or other statin therapy by their treating physicians, analysis will be
  conducted with 'time-under-statin' as a continuous or stratifying (categorical) predictor of
  change in the outcomes.
- Exclusion of ineligible participants: Secondary analyses will be conducted after exclusion of participants who were later found to have been ineligible at the time of randomization.
- Covariate-adjusted analysis: adjustment for baseline (pre-randomization) factors known to be associated with a particular outcome can increase the efficiency of the treatment effect comparison. Such factors will be identified from the literature and used as covariates in the trial outcome analyses.

Descriptive statistics will be used to determine the distribution of values for all variables, and variables requiring transformation to meet analytic assumptions will be appropriately transformed. Data analysis plans will be keyed to the specific aims as follows, and incorporate appropriate methodology as described below.

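### Section 8.6 makes inclusion in the analysis depend on remaining eligible and enrolled after randomization, which conflicts with the intention-to-treat primary analysis in Section 8.1

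*Protocol*

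**What the plan says.** Section 8.1 sets the principle: "The primary analytic approach for all trial outcomes will be intention-to-treat (ITT"). Among its secondary approaches it lists removal of ineligible participants: "Secondary analyses will be conducted after exclusion of participants who were later found to have been ineligible at the time of randomization". The primary analysis therefore keeps them.

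Section 8.6, the only section devoted to who is analyzed, reads: "All participants who remain eligible for and enrolled in the trial will be included in the analysis". It adds that their data are "analyzed by intention-to-treat in the group to which they were randomized unless otherwise specified".

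Section 5.3.2 lists reasons for which a participant may be withdrawn from the trial after randomization. One begins "Participant non-compliance with study visits, assessments and study drug such that data" and is limited to cases where the resulting data are missing or not valid despite the site's efforts. Another begins "Participant develops a medical or psychiatric condition that precludes full participation in" the study. Refusal to continue, an eating disorder and bariatric surgery are also listed.

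Stopping study drug is a different matter. Under Section 5.3.1 such participants "undergo expected tests and measurements through the planned completion date (24 months after randomization), unless indication for withdrawal from trial is also met". For sustained high LDL-C, Section 4.2.3 says: "The participant will continue to be enrolled in the trial and have all study measures, as per intention to treat".

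**The concern.** Intention-to-treat protects the comparison because membership of the analysis set is fixed at randomization. A set defined by who remains eligible and enrolled is fixed later, by events that treatment may influence. Assigning those who are left to their randomized arm does not bring back those who were removed.

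Two groups are at issue: participants withdrawn under Section 5.3.2, and participants judged after randomization not to be, or no longer to be, eligible. If either group differs between arms in a way related to PWV change, the primary slope comparison loses the protection of randomization. Section 8.6 also leaves open what happens to PWV values collected before withdrawal, which the repeated-measures analysis in Section 8.2 could use.

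**Working it through.** **1. The sections side by side**

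- *Participant found after randomization to have been ineligible.* Section 8.1 keeps this person in the primary analysis and removes them only in a secondary one. Section 8.6, read literally, removes them from every analysis, so the secondary analysis in Section 8.1 would have nothing left to exclude.
- *Participant withdrawn under Section 5.3.2.* Intention-to-treat in Section 8.1 includes this person. Section 8.6 does not, because the person is no longer enrolled.
- *Participant who stops study drug only.* Sections 4.2.3 and 5.3.1 keep this person enrolled and measured, so the enrollment condition in Section 8.6 removes nobody here.
- *Participant who stays in the trial but no longer meets an entry criterion.* Section 5.1 requires LDL-C below 160 mg/dL. Section 4.2.3 keeps participants who later exceed this in the trial under intention-to-treat. If remaining eligible means continuing to meet the entry criteria, Section 8.6 contradicts Section 4.2.3 as well.

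Section 8.4 also describes the primary analysis as falling within an intention-to-treat framework. Section 8.6 is the outlier.

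**2. The plan's own scale**

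Inputs from Section 8.2: SD 1.1 m/sec; within-participant correlation 0.5; times 0, 0.25, 0.5 and 1; two-sided alpha 0.05; power 0.85; drop-out 20%.

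- SS_t = 0.4375² + 0.1875² + 0.0625² + 0.5625² = 0.546875.
- Slope SD = √(1.1² × 0.5 / 0.546875) = 1.052, as stated.
- Target difference, Scenario 2: 0.693 − 0.315 = 0.378 m/sec.
- The two-sample calculation gives 140 per group, and 140 / 0.8 = 175, against 177 stated. The two-participant gap has no bearing on this point.

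**3. How large bias could be, on assumptions that are not in the protocol**

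Suppose there is no true effect and 177 per arm. A fraction f is removed from one arm only, and the removed participants' mean slope differs from that of the retained participants by s slope SDs. The retained mean then shifts by f × s × 1.052 m/sec. The standard error of the difference is 1.052 × √(1/[177(1 − f)] + 1/177).

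| f | s | Bias (m/sec) | % of 0.378 | Two-sided type I error |
|---|---|---|---|---|
| 5% | 0.25 | 0.013 | 3.5 | 0.052 |
| 5% | 0.5 | 0.026 | 7.0 | 0.056 |
| 10% | 0.5 | 0.053 | 13.9 | 0.074 |
| 20% | 0.5 | 0.105 | 27.8 | 0.144 |
| 20% | 1.0 | 0.210 | 55.7 | 0.426 |

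The table is a sensitivity range, not a forecast. One-sided removal is the unfavorable case, and 20% is its extreme end. If removal is balanced and unrelated to outcome, the bias is zero.

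**The case against.** The best defense is that Section 8.6 concerns screening. Under Section 5.5, participants consent and receive a study number at the screening visit, and those who fail screening are discontinued. Remaining eligible and enrolled could then mean having passed screening, and Section 8.6 would agree with Section 8.1. This is possible but strained. The sentence goes on to speak of the group to which participants were randomized. Section 4.2.3 uses continued enrollment for status during the trial, after randomization. Even on the kinder view, the text allows two populations.

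Other points on that side do stand:

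- Section 8.6 does not say only, names intention-to-treat, and allows for exceptions specified elsewhere.
- Section 8.5 monitors withdrawal by arm and plans sensitivity checks, with pattern-mixture models or multiple imputation as options. That fits poorly with deleting withdrawn participants, and suggests that the intent was full intention-to-treat.
- Section 8.6 does not expressly discard values already collected.
- The SAP, which is not at hand, may define the set properly. Section 8.6 would still need to agree with it.

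A reader might go further and infer that Section 8.6 amounts to an analysis of adherent completers. The protocol does not support this. Drug discontinuation does not end enrollment (Sections 4.2.3 and 5.3.1), nor does starting a statin, antihypertensive or insulin (Section 6.2.2). Adherence below 80% leads to counseling (Section 6.3). Withdrawal for non-compliance is discretionary and limited to cases without usable data.

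**Conclusion.** The inconsistency is real and sits within the protocol. Section 8.6 as written conditions the primary analysis on post-randomization status, while Section 8.1 makes intention-to-treat primary and exclusion of ineligible participants secondary. It affects participants withdrawn under Section 5.3.2 or judged no longer eligible.

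The consequence is a possible bias of unknown size and direction. The protocol says neither how many participants would be removed on these grounds, nor how removal would split by arm or relate to PWV. The range in the working, 0.013 to 0.210 m/sec against a target of 0.378, rests wholly on its stated assumptions.

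Three stronger inferences should not be drawn:

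- *That the whole 20% drop-out allowance would be removed by Section 8.6.* That figure is a planning allowance, which Section 5.4 calls conservative. Drop-outs lack later data under any analysis set.
- *That the treatment effect would be overstated by a set amount.* This needs assumed outcomes for those who leave, and keeping them in the set would not by itself supply their missing later values.
- *That the population would be chosen after unblinding.* Nothing in the protocol indicates this, and Section 8.1 refers the detail to a separate SAP.

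**What to change.** Replace the sentence in Section 8.6 with:

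> All randomized participants are analyzed in the arm to which they were randomized, regardless of later eligibility, adherence or withdrawal, using every PWV value collected, including values before withdrawal and after study-drug discontinuation.

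Keep exclusion of participants ineligible at randomization as the secondary analysis already listed in Section 8.1, and check that the SAP uses the same definition. This agrees with Sections 4.2.3, 5.3.1, 8.1 and 8.4. The cost is one sentence in the protocol and matching SAP wording, with no extra participants, visits or data and no change to the 177 per group.
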